#### 16.1.1.1. eCOA Compliance

Overall electronic diary (eCOA) compliance (across all eCOAs and all participants) for the study is calculated as:

Where the expected number of complete eCOAs per participant is defined as 43, the number of days in which the eCOA is expected to be completed. This definition will also apply to participants who discontinue the study early.

An eCOA is considered complete if there is no missing data within the assessment. Solicited event data reported by the investigator will not contribute to eCOA compliance. On days when the option to select "no symptoms to report" is available and there are no occurrences of the symptoms solicited for on that day, an eCOA will be considered

Analysis Plan Page 48 of 57

complete if the temperature result is available.

A participant is considered to be compliant with their eCOA if at least 80% of their eCOA are complete, i.e, a participant is compliant if they meet the following criteria:

$$\frac{Total\ number\ of\ complete\ eCOAs}{Expected\ number\ of\ complete\ eCOAs}$$
 × 100 ≥ 80%

The overall compliance, and the number of participants who are 0 - <50% compliant, 50 - <80% compliant and ≥80% compliant with eCOA assessments will be summarized.

#### 16.1.2. Unsolicited AEs, including SAEs

For each study intervention, the incidence rates (frequencies and percentages) of participants/events with unsolicited AEs (any, related, grade 3, leading to medical attention and related grade 3 respectively), including serious AE, occurring within 43-days (Days 1-43) post-dose of study interventions will be presented by SOC and PT. The incidence rates of participants/events with any unsolicited AEs will be repeated and summarized by country.

#### 16.1.2.1. Relationship to Study intervention

Causality, as indicated by the Investigator is classed as "related" and "not related" to MMRVNS/MMRV. A "related" AE is defined as an AE with a relationship to study intervention as "related". If a participant reports the same AE more than once within that SOC/PT, the AE with the worst-case relationship to study intervention will be used in the corresponding relationship summaries for each study intervention.

#### 16.1.3. Unsolicited AEs, Excluding SAEs

For each study intervention, the incidence rates (frequencies and percentages) of participants/events with unsolicited

Analysis Plan Page 49 of 57

AEs, excluding serious AE, occurring within 43-days (Days 1-43) post-dose of study interventions will be presented by SOC and PT.

Immediate unsolicited AE is defined as an unsolicited AE that occurred within 30 minutes of vaccination. The immediate unsolicited AE flag is derived as follows: If the AE does not occur on the day of vaccination the flag is set to 'N'. Otherwise, if the AE occurs on the day of vaccination but happened before the vaccination then the flag is also set to 'N'. Otherwise, if the AE occurs on the day of vaccination and AE DATETIME minus Vaccination DATETIME is <= 30 minutes then set the flag to 'Y'. Otherwise, if the AE occurs on the day of vaccination and did not happen before the vaccination but either the time of vaccination or time of the AE is missing, then flag is set to 'U'. If the time of the AE is set to "00:00", then it will be assumed to be unknown and will be handled as missing. Immediate unsolicited AEs will be flagged in the listings.

#### 16.1.4. Serious AEs

[figure not shown]
For each study intervention, the incidence rates (frequencies and percentages) of participants with SAE occurring post-dose of study interventions will be presented by SOC and PT. Similar tabulation will be done for SAE with causal relationship to vaccination as assessed by the investigator; for fatal SAE and for causally related fatal SAE. Serious AEs will be recorded on the "Expedited Adverse Events" page of the eCRF. The incidence rates of participants with serious AEs will be repeated and summarized by country.

Listings of AEs and SAEs leading to discontinuation of study will be provided.

#### 17. DATA NOT SUMMARIZED OR PRESENTED

The other variables and/or domains not summarized or presented are:

Physical Examination

Analysis Plan Page 50 of 57

These domains and/or variables will not be summarized or presented, but will be available in the clinical study database, SDTM and/or ADaM datasets.

Analysis Plan Page 51 of 57

## APPENDIX 1. PROGRAMMING CONVENTIONS FOR OUTPUTS

## **IQVIA Output Conventions**

Outputs will be presented according to the following IQVIA Output Conventions

**Document Headers** 

All TFL is to include the following header:

**GSK Vaccines** 

Vaccine: MMRVNS and MMRV

Study 217715 (MMRVNS 20-001) - DELIVERY DESIGNATION

where delivery designation is the name of the current delivery, e.g., DRY-RUN, FINAL ANALYSIS REPORT, etc

#### **Dates & Times**

Depending on data available, dates and times will take the form yyyy-mm-dd Thh:mm:ss.

## **Spelling Format**

English US

## **Presentation of Intervention Groups**

For outputs, intervention groups will be represented as follows and in the given order:

Intervention Group	For Tables and Graphs	For Listings
MMRV(H)NS	MMRV(H)NS	MMRV(H)NS

Analysis Plan Page 53 of 57

Intervention Group	For Tables and Graphs	For Listings
MM(H)RVNS	MM(H)RVNS	MM(H)RVNS
M(L)M(L)R(L)V(L)NS	(MMRV)(L)NS	(MMRV)(L)NS
MMRV_Lot1	MMRV	MMRV Lot1
MMRV_Lot2		MMRV Lot2

#### **Presentation of Visits**

For outputs, visits will be represented as follows and in that order:

Short Name	Long Name
Visit 1	Visit 1 (Day 1)
Visit 2	Visit 2 (Day 15)
Visit 3	Visit 3 (Day 43)
Safety Follow-up	Safety Follow-up (Day 181)

## Listings

All listings will be ordered by the following (unless otherwise indicated in the template):

 Randomized study intervention (or intervention received if it's a safety output), first by active dose [by ascending dose group] and then control

Analysis Plan Page 54 of 57

- Center-participant ID,
- Date (where applicable).

#### **Decimal places**

Decimal places for categorical data

- For percentages one decimal will be displayed
- Differences in percentages and their corresponding confidence limits will be displayed with one more decimal
  than the maximum number used to display the individual percentages, for example the difference between two
  percentages displayed with one decimal will be displayed with two decimals.
- Decimal places for Demographic and baseline characteristics will be as follows:

The mean, median, and standard deviation for continuous baseline characteristics (age) will be presented with one decimal.

Serological Summary Statistics

The number of decimals used when displaying geometric mean concentrations (GMC) and their confidence limits is shown in the following table:

GMC value	Number of decimals
<0.1	3

Analysis Plan Page 55 of 57

GMC value	Number of decimals
>=0.1 and <10	2
>=10 and <1000	1
>=1000	0

- When multiple categories of GMC values are present in the same table, the number of decimals displayed should match that of the smallest category (i.e. the one with the higher number of decimals). For example, if GMC values of <0.1 appear in the same table as values of >=0.1 and <10 3 decimals should be displayed for both.

- GMC ratios and their confidence limits will be displayed with 2 decimals regardless of the actual values.

## APPENDIX 2. PARTIAL DATE CONVENTIONS

Imputed dates will NOT be presented in the listings.

When partially completed dates (i.e. with missing day or month) are used in calculations, the following standard rules will be applied:

- A missing day will be replaced by 15
- A missing day and month will be replaced by June 30th.

The following exceptions apply:

Analysis Plan Page 56 of 57

- Adverse event start dates with missing day:
- o If the event starts in the same month as the study intervention, the contents of AE.AESTRTPT (the flag indicating if the event occurred before or after vaccination) will be used to complete the date. If 'after vaccination' is selected, the imputed start date will match study dose given during that month. If 'before vaccination' is selected, the imputed date will be one day before the study intervention given during that month.
- Adverse event start dates with missing day and month:
- If the event starts in the same year as study intervention, the contents of AE.AESTRTPT (the flag indicating if the event occurred before or after vaccination) will be used to complete the date. If 'after vaccination' is selected, the imputed start date will match the study intervention given during that year. If 'before vaccination' is selected, the imputed date will be one day before the) study intervention given during that year.

If the imputed start date falls after the event end date, the imputed start date will be adjusted to be the end date minus 1 day.

All other cases of incomplete AE or concomitant medication/vaccination start date will follow the standard rules above.

Analysis Plan Page 57 of 57

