#### 16.1. Adverse Events

Adverse Events will be coded using MedDRA central coding dictionary, Version 27.0 or higher. Adverse events will be described using frequency and percentage.

Adverse Events will be grouped by SOC and PT and summarized by study intervention at time of onset of the AE.

The summary tables will present the number and percentage of total participants and number of events, by SOC and by PT for each study intervention.

For the summaries of AEs, participants who experience the same AE (in terms of the MedDRA SOC and PT) more than once will only be counted once for that event in the number of participants but all occurrences of the same event will be counted in the number of events.

See APPENDIX 2 for handling of partial dates for AEs. In the case where it is not possible to define an AE as pretreatment or treatment-emergent (TEAE) due to missing or partial dates, the AE will be classified by the worst case; i.e., TEAE. TEAE are defined as AEs which commence on or after the time of the study intervention through to the study end. All AE summaries will be restricted to TEAEs only.

Listings of all AEs and SAEs leading to discontinuation from the study will be provided.

Analysis Plan Page 43 of 57

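### On their literal text, the SAP's partial-date rules can place an AE flagged as after vaccination before the dose, or move a Day 1–43 onset past Day 43

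*SAP*

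**What the plan says.** SAP Appendix 2 gives two standard rules, which apply "When partially completed dates (i.e. with missing day or month) are used in calculations":

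- "A missing day will be replaced by 15".
- "A missing day and month will be replaced by June 30th".

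AE start dates have exceptions that use a flag for onset before or after vaccination. With the flag at after vaccination:

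- Day missing, onset in the dosing month: "the imputed start date will match study dose given during that month".
- Day and month missing, onset in the dosing year: "the imputed start date will match the study intervention given during that year".

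Other incomplete AE starts fall back on the standard rules. AE end dates have no exception. A last step covers conflicts: "If the imputed start date falls after the event end date", then "the imputed start date will be adjusted to be the end date minus 1 day".

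These dates feed the safety tables. SAP 16.1 defines a TEAE by onset at or after the dose up to study end, treats an AE as a TEAE when missing or partial dates make classification impossible, and states: "All AE summaries will be restricted to TEAEs only". The unsolicited AE tables in 16.1.2 and 16.1.3 count Days 1–43. The SAE tables in 16.1.4 run from the dose onward without that limit.

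**The concern.** The appendix uses the investigator's flag to place an event on the dose date, and a later step can undo that. Nothing holds the adjusted start at or after dosing, and nothing keeps a partial start that may belong to Days 1–43 inside that window. Two things can follow:

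1. An unsolicited AE known to have begun after vaccination gets a pre-dose start and drops out of the TEAE-only summaries, against its flag and against the worst-case intent of 16.1.
2. An AE with true onset in Days 1–43 gets a start after Day 43 and drops out of the tables for the secondary endpoint on unsolicited AEs.

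Neither would be easy to spot, because the appendix keeps imputed dates out of the listings.

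**Working it through.** The documents give no figure on this point, so there is nothing to reproduce. The rules were applied as written.

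**Inputs.** The imputation rules come from SAP Appendix 2. Study Day comes from SAP 6.1: event date − dose date + 1 on or after the dose, and event date − dose date before it. Day 43 is therefore dose + 42 days. The TEAE definition is in SAP 16.1 and the Day 1–43 window in 16.1.2 and 16.1.3.

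**Limb 1: moved before the dose.** This needs an end date that is itself partial.

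| Dose | Recorded start (flag: after) | Recorded end | Imputed start | Imputed end | Final start | Study Day |
|---|---|---|---|---|---|---|
| 20 Jan | Jan, no day | Jan, no day | 20 Jan | 15 Jan | 14 Jan | 14 − 20 = −6 |
| 10 Sep | year only | year only | 10 Sep | 30 Jun | 29 Jun | −73 |
| 20 Jan | Jan, no day | 25 Jan (complete) | 20 Jan | – | 20 Jan | 1 |

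When both days are missing and both dates fall in the dosing month, every record dosed on the 16th or later is reset to the 14th. A dose on the 15th does not trigger the step, because the start must be later than the end.

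**Limb 2: moved past Day 43.**

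| Dose | True onset | Recorded start | Recorded end | Final start | Study Day |
|---|---|---|---|---|---|
| 25 Jan 2023 | 2 Mar (Day 37) | Mar, no day | ongoing | 15 Mar | 49 + 1 = 50 |
| 25 Jan 2023 | 2 Mar (Day 37) | Mar, no day | 6 Mar | 5 Mar | 40 |
| 10 Dec 2023 | 5 Jan 2024 (Day 27) | 2024 | ongoing | 30 Jun 2024 | 204 |
| 10 Dec 2023 | – | 2024 | 8 Jan 2024 | 7 Jan 2024 | 29 |

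The second and fourth rows show that the end-date step, which causes limb 1, pulls a limb 2 event back inside the window when a complete, early end date exists.

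**Size.** Assumptions: every dose date in 2023 equally likely, onset equally likely on Days 1–43, durations of 1–7 days equally likely. Where two figures appear, they differ by whether the first day counts towards the duration.

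| Records | Share affected |
|---|---|
| Limb 1: both days missing, both dates in the dosing month | 20–22% |
| Limb 1: all records with both days missing | about 6% |
| Limb 1: valid complete end date | 0% |
| Limb 2: later-month start lacking the day, end absent or lacking the day | 12.7% |
| Limb 2: later-month start lacking the day, end complete | 3.4–4.6% |

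The limb 1 share is below one half because onset and end both fall in the dosing month more often when dosing is early in that month.

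A second enumeration, with all flagged Day 1–43 onsets as the denominator and fixed durations, points the same way. With both days missing, 9.7–9.8%, 6.4%, 3.1% and 0.2% move before the dose for durations of 0, 3, 7 and 14 days. With start and end both year only, about 41–45% do.

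**The case against.** The strongest reply is that limb 1 depends on a reading. The adjustment compares an imputed start with the event end date, without calling that end imputed, and the closing sentence of the exceptions mentions only incomplete start dates. If only recorded, complete end dates are compared, limb 1 vanishes for valid data. But the standard rules cover any partial date used in a calculation and do not exempt AE end dates, so the literal text supports the reading used here. At the least, a programmer must choose.

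A second reply is that the worst-case rule in 16.1 keeps the event as a TEAE. That rule applies when classification is impossible. Once Appendix 2 has produced a date, it is not clearly triggered, and it would not return an event with a negative Study Day to the Day 1–43 tables.

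Several stronger inferences do not stand:

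- **That limb 2 also breaks the worst-case TEAE rule, or removes the event from all AE summaries.** An event imputed to Day 50 or Day 204 is still a TEAE, because the definition runs to study end. It leaves only the Day 1–43 unsolicited tables, and an SAE stays in the SAE tables.
- **That a year-only onset in the year after dosing always passes Day 43.** It does with no end date or a year-only end date. A complete early end date can bring it back, as the 8 January example shows.
- **That the rules only ever undercount.** A year-only start in the dosing year flagged as after vaccination goes to Day 1, so an SAE with true onset after Day 43 can enter the 43-day tables, which include SAEs.

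It also stands that materiality is low. Solicited events come from dated diaries, the plan makes no statistical safety comparison between groups, and the same rules apply to every group.

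**Conclusion.** The point holds as a minor defect in a stated rule. Limb 1 gives a wrong result on the literal text: an event recorded as after vaccination receives a pre-dose start and leaves the TEAE-only summaries. It requires a partial (or erroneous) end date. Limb 2 also follows from the text, but its effect is confined to the Day 1–43 unsolicited AE tables.

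The percentages in the working rest on assumed uniform dosing and onset dates and on assumed durations. They are shares of AEs with the stated kind of partial date, not of all AEs. The documents do not say how many such AEs to expect. They are probably rare, so absolute counts should be small, and no conclusion of the trial is likely to turn on this.

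**What to change.** Add to SAP Appendix 2:

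1. When the flag says after vaccination, an imputed AE start may not precede the dosing date, including after the end-date adjustment, and a partial AE end date may not be imputed to before dosing. The 20 January example then stays at 20 January, Day 1.
2. For an onset flagged as after vaccination in a later month or year than the dose, impute the earliest date that fits the recorded part and is on or after dosing. The 25 January example with a March start becomes 1 March, Day 36. The medication table in the same appendix already takes the earliest compatible date for partial starts.

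The cost is about two lines of text and a small program change. The downside is that a few events with true onset after Day 43 may be counted inside the window, which is the conservative direction for safety.

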## **Algorithm for Prior / Concomitant Medications:**

START DATE	STOP DATE	ACTION
Known	Known	If start date < study med start date, assign as prior  If start date >= study med start date and start date <= end of intervention, assign as concomitant
Partial	Known/Partial/	Impute start date as earliest possible date (i.e. first day of month if day
	Missing	unknown or 1st January if day and month are unknown), then:
		If start date < study med start date, assign as prior
		If start date >= study med start date and start date <= end of intervention,
		assign as concomitant
Missing	Known/Partial/	If start date < study med start date, assign as prior
	Missing

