#### 13. MEDICATIONS

The percentage of participants who started medications after study intervention will be presented by study intervention for the ES. Medications will be presented by Anatomical Therapeutic Chemical (ATC) classification and preferred drug name and by study intervention.

See APPENDIX 2 for handling of partial dates for medications, in the case where it is not possible to define a medication as prior or concomitant, the medication will be classified by the worst case; i.e., concomitant.

- 'Prior' medications are medications which started prior to the dose of study intervention.
- 'Concomitant' medications are medications which started on or after the day of the administration of study intervention.

Further details are in Section 6.8 of the Protocol. Concomitant medications which started from Day 1 to Visit 3 blood sample will be presented in table summaries (Any, antipyretic action) and in listings for all medications.

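### For a medication whose partial start date could fall on either side of the dose, the SAP Appendix 2 algorithm always returns prior, where SAP Section 13 says concomitant (low severity)

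*SAP*

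**What the plan says.** The SAP gives three rules that bear on a medication with an incomplete start date.

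- **Section 13 (Medications).** Prior means started before the dose; concomitant means started on or after the day of the dose. The sentence that refers to Appendix 2 for partial dates adds that, where status cannot be defined, "the medication will be classified by the worst case; i.e., concomitant". The same section fixes the output: "Concomitant medications which started from Day 1 to Visit 3 blood sample will be presented in table summaries", for any medication and for those with antipyretic action. All medications go into listings.
- **Appendix 2, algorithm for prior and concomitant medications.** For a partial start date: "Impute start date as earliest possible date", meaning the first of the month, or 1 January if the month is also unknown. The record is prior if that date is before the dose. Otherwise: "If start date >= study med start date and start date <= end of intervention, assign as concomitant".
- **Appendix 2, standard rules.** "A missing day will be replaced by 15"; "A missing day and month will be replaced by June 30th". The closing sentence extends them to medications: "All other cases of incomplete AE or concomitant medication/vaccination start date will follow the standard rules above".

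Adverse events have their own exception. If the day is missing, the month is the dosing month and the event is flagged as after vaccination, "the imputed start date will match study dose given during that month".

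The SAP modification history for version 3.0 records an update meant to bring Appendix 2 into line with Section 13, so agreement between the two was intended.

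**The concern.** The three rules can put the same record in different categories, so two programmers who each follow the SAP could produce different medication tables. The most specific rule, the algorithm, also works against the SAP's own worst-case principle: it moves indeterminate medications out of the concomitant tables.

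The records concerned are those whose known date parts allow a start before or after the dose: the dosing month with the day missing, or the dosing year with day and month missing. Partial dates clearly before or clearly after the dose are classified correctly.

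Two side effects follow. First, an adverse event and its treatment can be separated: with the same partial date, the event flagged as after vaccination is dated to the dosing day, while the medication is dated to the first of the month and becomes prior. Second, the algorithm limits concomitant to starts no later than an end of intervention that the SAP does not define. Section 13 has no such limit, and Protocol Section 7.1 describes a single-dose study.

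**Working it through.** There is no planned figure to reproduce; this is a check of a classification rule.

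**Step 1, logic.** Let E and L be the earliest and latest dates that the known parts allow, and D the dose date. The record is ambiguous only if E < D ≤ L. The algorithm sets start = E and returns prior if E < D. Every ambiguous record meets that condition, so the result is prior in 100% of them. Under Section 13 it is concomitant in 100%.

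**Step 2, dose dates.** All 365 dates of 2023 were taken as possible dose dates with equal weight (an assumption).

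| Record | Ambiguous dose dates | Prior: algorithm | Prior: 15th / 30 June rule | Prior: Section 13 |
|---|---|---|---|---|
| Dosing month, day missing | 353 | 353 | 185 | 0 |
| Dosing year, day and month missing | 364 | 364 | 184 | 0 |

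The other 12 dates in the first row are doses on the 1st of a month, where a start in that month cannot precede the dose (365 − 12 = 353). In the second row only a 1 January dose is unambiguous (365 − 1 = 364). The standard rules leave 353 − 185 = 168 and 364 − 184 = 180 dates as concomitant, so they agree with neither of the other two rules.

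**Step 3, true post-dose starts with the day missing.** Each dose date is paired with each start day in the window. The record is prior under the algorithm if the 1st of the start month is before D, and prior under the standard rule if the 15th is before D.

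| True start | Pairs | Prior: algorithm | Prior: 15th rule |
|---|---|---|---|
| Days 1-4 | 365 × 4 = 1,460 | 1,340 (91.8%) | 668 (45.8%) |
| Days 1-15 | 365 × 15 = 5,475 | 4,035 (73.7%) | 1,516 (27.7%) |
| Days 1-43 | 365 × 43 = 15,695 | 5,373 (34.2%) | 1,523 (9.7%) |

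Over Days 1-43 the algorithm therefore classifies 100 − 34.2 = 65.8% of missing-day starts correctly. The 2024 calendar changes these percentages by no more than 0.2 points.

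**Step 4, cost of the opposite rule.** Take true starts 1-30 days before the dose with the day missing: 365 × 30 = 10,950 pairs. With a stop-date check, a record is wrongly counted as concomitant if its start month ends on or after D and its stop date (start + duration − 1) is not before D. For assumed courses of 3, 7 and 14 days this gives 694, 1,938 and 3,653 records, or 6.3%, 17.7% and 33.4%. With no stop date it is 5,373, or 49.1%.

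**Step 5, the upper limit.** With Visit 3 on nominal Day 43, 5,373 of the 15,695 Day 1-43 missing-day starts (34.2%) have a start month that runs past Visit 3. A corrected rule must therefore say how a partial date is compared with the Visit 3 blood sample.

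**The case against.** The best defence is to read Section 13 as a sequence: apply Appendix 2 first, and use the worst case only for what is still unclassified, such as a fully missing start date. That reading is possible, and the version 3.0 entry is compatible with it. It does not remove the problem. The clause would then never act on a partial start date, although it stands in the sentence about partial dates, and the two parts of Appendix 2 would still impute different dates for one medication. A specific algorithm would normally override a general convention, but the closing sentence of the standard rules names medication start dates, so the SAP should say which applies.

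Other objections stand and limit the point:

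- Only descriptive tables are touched, and the records remain visible in the listings.
- Protocol Section 6.8 asks for start and end dates, and the Schedule of Activities has medications recorded on Day 1, at the Day 2-3 call, on Day 15 and on Day 43. A missing day should be uncommon, least likely of all on Days 1-4, where the percentage is highest.
- Every percentage is conditional on a missing day and is calendar arithmetic, not an estimate of records lost.
- The algorithm's row for a fully missing start date may be cut off in the available text, so nothing is concluded about it.

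**Conclusion.** Wrong as written, low severity. The algorithm's result for ambiguous partial start dates is the reverse of Section 13's worst case, and this follows from logic without any assumption. The consequence is an undercount of post-dose medications in the Day 1-to-Visit 3 tables (any, antipyretic), by an amount the documents do not allow one to estimate. The conditional percentages rest on dose dates spread evenly over 2023 and, within each window, evenly spread start days.

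A reader might infer that about nine in ten early post-dose medications would be lost, or that the immunogenicity results are exposed. The documents support neither. The 91.8% applies only to Day 1-4 starts recorded without a day. The GMC and seroresponse analyses do not use the prior/concomitant label. Per Protocol Set elimination for medication refers to the restrictions in Protocol Section 5.2.2, and nothing in the SAP ties it to this algorithm.

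**What to change.** In the algorithm's row for partial start dates, replace the action with:

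> If the known parts of the start date, or the stop date or its known parts, show that the medication started or ended before the date of study intervention, classify as prior; otherwise classify as concomitant. A concomitant medication with a partial start date is included in the Day 1-to-Visit 3 tables unless the known parts show a start after the Visit 3 blood sample. The 15th and June 30th rules do not apply to this classification.

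Replace the undefined end-of-intervention limit with the Visit 3 blood sample for the tables, in line with Section 13. Check that the row for a fully missing start date also agrees with Section 13.

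The change is to SAP wording and the matching program; no data collection changes. The price is that some truly prior medications are counted as concomitant: the 6.3% to 33.4% in Step 4 for assumed 3- to 14-day courses, all still in use on the dosing day, and 49.1% if the stop date is also unknown. Section 13 already accepts error in that direction. Some starts after Visit 3 with a missing day may also enter the tables.
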